• Official Title: Use of Two Dissolvable Therapeutics Under Removable Partial Dentures: Reported Effects on Denture Comfort, Retention, and Dry Mouth Conditions

• NCT Number: NCT05441527

• Document Date: May 28, 2024

Objective: The primary aim of the present study is to quantify the change in a patient's saliva buffering capacity when MI Paste and Biotene Dry Mouth Gel is used under a removable prosthesis.

Design: This is a randomized, case-crossover study (*ClinicalTrials.gov identifier-NCT05441527*). The study population consists of adult subjects (ages 18-99) had a removable prosthesis (e.g., partial denture, complete denture that was made at the University of Iowa College of Dentistry and Dental Clinics (primarily the Family Dentistry Clinic and the Prosthodontics Clinics) within the past 10 years. Subjects cannot have any of the following criteria: casein (i.e., protein found in milk or other dairy products) allergy, lactose intolerance, multiple food or cosmetic ingredient allergies in their health history, ill-fitting dentures that need to be remade or relined.

Methods: Consented subjects will be randomly assigned to Group A or Group B. Randomization will be done as 1:1, in which subjects will have a 50% chance of being assigned to Group A (i.e., use MI Paste during the first week, use Biotene Dry Mouth Gel during the second week) or a 50% chance of being assigned to Group B (i.e., use Biotene Dry Mouth Gel during the first week, use MI Paste during the second week). Once a subject completes using the first product, they will voluntarily complete the questionnaire and be instructed to switch to the next product. Once the subject completes the second product, they will voluntarily complete the questionnaire.

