Statistical Analysis Plan: The primary outcomes are: (i) change from baseline in patient comfort for MI Paste as assessed by numerical scale, (ii) change from baseline in patient comfort for Biotene Dry mouth gel as assessed by numerical scale, (iii) change from baseline in retention for MI Paste as assessed by numerical scale, (iv) change from baseline in retention for Biotene Dry Mouth Gel as Assessed by Numerical Scale. Descriptive statistics will be conducted to depict all the variables in the study. A paired-sample t-test or a Wilcoxon signed-rank test as appropriate will be used to detect the difference in saliva buffering capacity between pre- and post-MI paste application. Moreover, McNemar's test or 4 Bowker's test of symmetry will be used to compare the denture fit and function and dry mouth relief between pre- and post-MI paste application. All tests utilize a significance level of 0.05, and statistical analyses will be performed using the statistical package SAS® System version 9.4 (SAS Institute Inc., Cary, NC, USA).

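### For rating items with three or more ordered levels, Bowker's test of symmetry ignores order and direction and is less powerful than a paired ordinal test; the loss is severe on longer scales with few subjects

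*Combined protocol and SAP*

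**What the plan says.** The Statistical Analysis Plan gives one sentence to these items. It offers McNemar's test or Bowker's "test of symmetry will be used to compare the denture fit and function and dry mouth relief between pre- and post-MI paste application". (The 4 printed before Bowker's name looks like a stray page number from text extraction, and nothing is made of it here.) The level is common to every test: "All tests utilize a significance level of 0.05".

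For fit, function and dry mouth relief, the plan does not give the response format, the number of categories, whether they are ordered, or a rule for choosing between the two tests. A numerical scale is mentioned only for comfort and retention, for example "change from baseline in patient comfort for MI Paste as assessed by numerical scale". No sample size, effect size or target power appears anywhere.

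A paired test that uses order is already in the plan, for a different endpoint: "A paired-sample t-test or a Wilcoxon signed-rank test as appropriate will be used to detect the difference in saliva buffering capacity".

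**The concern.** With two categories, Bowker's test is McNemar's test. Naming it separately therefore matters only if the plan expects items with three or more categories. Fit, function and relief run from worse to better, so those categories are very likely ordered, and the question is whether ratings improved.

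Bowker's null hypothesis is that every pair of mirror-image cells in the before/after table is balanced. It spreads its degrees of freedom over all such pairs, treats a one-step change and a four-step change as unrelated, and has no direction. At stake is how to read the result: a null finding may reflect the test rather than the product, and a significant p-value does not by itself indicate improvement. The point concerns only what the named test tests, not which outcomes or products are covered.

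**Working it through.** **Inputs from the documents.** Paired before/after comparison; level 0.05 (taken as two-sided).

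**Assumed, because the documents are silent.** Ordered items with k levels; N subjects; a latent bivariate normal cut at equal-probability baseline thresholds; correlation 0.5; shift 0.5 SD; no dropout. There is no planned power figure to reproduce.

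**1. Algebra (no assumption about N).** With n_ij the number going from level i to level j:

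Q = Σ over i<j of (n_ij − n_ji)² / (n_ij + n_ji), with df = k(k−1)/2.

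- df is 3 for k = 3, 10 for k = 5 and 55 for k = 11.
- Swapping before and after leaves Q unchanged, so it has no direction.
- Relabelling the categories leaves Q unchanged, so it uses no order.
- Each term is at most n_ij + n_ji, so Q cannot exceed the number of subjects who change category. The 5% critical values are 7.81, 18.31 and 73.31. With full df, rejection therefore needs at least 8, 19 and 74 changers at k = 3, 5 and 11, even if every one of them improves.

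**2. Significant with no net shift.** Take 30 subjects on a 3-level item: 6 go 1→2, 6 go 2→3, 6 go 3→1, and 12 do not change. The margins are 10/10/10 before and after.

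- Bowker: three pairs of (6, 0), each 6²/6 = 6, so Q = 18.0 on 3 df, p = 0.0004.
- Signed-rank: 12 changes of +1 share rank 6.5 (sum 78); 6 changes of −2 share rank 15.5 (sum 93). The expected sum is 18×19/4 = 85.5. The tie-corrected variance is 18×19×37/24 − [(12³−12) + (6³−6)]/48 = 527.25 − 40.125 = 487.125, so SD = 22.07. Then z = (93 − 85.5)/22.07 = 0.34, p = 0.73.

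**3. Power by simulation.** There were 4,000 replicates per row. Bowker is shown with full df, then with df counting only non-empty cell pairs. The signed-rank test uses the tie-corrected normal approximation with zeros dropped. Shift 0.5 SD, correlation 0.5:

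| Levels | N | Bowker | Signed-rank |
|---|---|---|---|
| 3 | 30 | 31% / 31% | 56% |
| 3 | 60 | 69% / 69% | 86% |
| 4 | 60 | 56% / 57% | 90% |
| 5 | 30 | 3% / 8% | 66% |
| 5 | 40 | 11% / 17% | 78% |
| 5 | 60 | 38% / 42% | 92% |
| 5 | 100 | 80% / 81% | 99% |
| 11 | 60 | 0% / 1% | 94% |

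A fresh run of every row except the 5-level, N = 100 one agreed within 3 percentage points.

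**4. Sensitivity.** Bowker's power rises with a larger shift or correlation. At 0.8 SD it is 72% (3 levels, N = 30), 78% (4 levels, N = 40) and 91–93% (5 levels, N = 60). At 0.5 SD with correlation 0.7 it is about 85% (3 levels, N = 60) and 57–67% (5 levels, N = 60). It stayed below the signed-rank test in these settings.

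**5. Size.** With no shift and full df, Bowker rejected 1.8% of the time (3 levels) and 0.0% (5 levels) at N = 20. It is conservative there, not inflated.

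**The case against.** The strongest reply is that the premise is inferred. The documents do not say that these items have three or more levels, or that the levels are ordered. If an item is yes/no, McNemar's test applies and is suitable. This stands, and it limits the point to multi-level ordered items. It does not remove the point, because Bowker's test has no separate role for binary items.

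A reader might infer that Bowker's test has almost no power in this trial, or will usually miss a real improvement. The documents do not support that. N, number of levels and effect size are all unstated, and at 3 or 4 levels with N = 60, or with a larger shift, the test more often rejects than not. The 11-level row is illustrative only, since nothing says these items use such a scale.

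The cyclic table is contrived to cancel exactly. It shows what the test can do, not what is likely. The plan also promises descriptive statistics for all variables, which would show the direction of change even though the p-value does not.

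Finally, the signed-rank test has its own assumption: ranking the sizes of changes treats category steps as comparable, which is debatable for verbal categories.

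**Conclusion.** The point holds for items recorded with three or more ordered levels. That Bowker's test uses no order and no direction is algebra and needs no assumed figures. The size of the power loss rests on the assumptions listed. It is severe at about 5 or more levels with roughly 40 or fewer subjects and a moderate shift, and smaller at 3–4 levels, with more subjects or with a larger shift.

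Two further inferences should be resisted. The test is not invalid: it is a proper test of its own null hypothesis and does not inflate type I error. Nor does the sentence, as worded, name the listed primary outcomes of comfort and retention, so the point should not be read as undermining those.

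**What to change.** First state, for each questionnaire item, the response scale and number of levels. Then replace the sentence with, for example:

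*Items on denture fit, denture function and dry mouth relief that are recorded with three or more ordered levels will be analysed as recorded, without collapsing, by the Wilcoxon signed-rank test of within-subject change, with the Hodges–Lehmann estimate of change and its 95% confidence interval. Items recorded as yes/no will be analysed by McNemar's test.*

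Drop Bowker's test for ordered items.

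**Cost.** A few lines of the SAP and no new data. The signed-rank test is already planned for saliva buffering capacity; the interval may need a little extra SAS code. The small downside should be acknowledged: steps between categories are treated as comparable, and the Hodges–Lehmann estimate is coarse on very short scales, so the before/after table should be reported beside it.

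### The only named dry mouth test compares relief before and after MI Paste, but no pre-MI Paste value is defined and a one-product pre/post test cannot separate a product effect from expectation

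*Combined protocol and SAP*

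**What the plan says.** The Statistical Analysis Plan paragraph names McNemar's or Bowker's test to "compare the denture fit and function and dry mouth relief between pre- and post-MI paste application". No other named test concerns dry mouth, and none of the named tests compares MI Paste with Biotene. On error level it says only: "All tests utilize a significance level of 0.05".

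The Methods paragraph places questionnaires at two points. After the first product: "Once a subject completes using the first product, they will voluntarily complete the questionnaire and be instructed to switch to the next product". After the second: "Once the subject completes the second product, they will voluntarily complete the questionnaire". It describes no questionnaire before the first product. Group B is to "use Biotene Dry Mouth Gel during the first week, use MI Paste during the second week", and no washout is described.

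The SAP does imply a baseline rating for comfort and retention, for example "change from baseline in patient comfort for MI Paste as assessed by numerical scale". It mentions no baseline for dry mouth. The wording of the relief item, its categories and its reference period are not given, and neither document section describes blinding.

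**The concern.** McNemar's and Bowker's tests need the same item recorded twice per subject. Relief, in its ordinary sense, is a judgement of change after using something, so it has no natural value before MI Paste is used. The documents do not say which record supplies the pre value. It could be a rating at an undescribed baseline, the post-Biotene questionnaire (available before MI Paste only in Group B), or a default of no relief. These choices give tests of different hypotheses with very different error rates.

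Dry mouth is in the trial's title. If the analyst defaults to no relief, a significant p-value could mean only that a handful of subjects ticked relief. Even with a proper pre-product rating, the contrast has no comparator, so expectation in subjects who know which product they are using would be counted as effect.

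**Working it through.** **Inputs.** From the documents: significance level 0.05 (sidedness not stated; two-sided assumed), a paired McNemar or Bowker test, 1:1 allocation to two sequences, and questionnaires after each product. The plan gives no sample size, power or relief rate, so there is no figure to reproduce. Assumptions: binary item, N from 10 to 60, MI Paste inert, and a proportion p who report relief for non-specific reasons. Bowker's test on more categories has more degrees of freedom and was not calculated.

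**Step 1: threshold if every pre value is no relief.** All k discordant pairs point the same way.
- Exact McNemar: p-value = 2 × 0.5^k. k = 5 gives 0.0625; k = 6 gives 0.031.
- Uncorrected chi-square: (k − 0)²/k = k, against 3.84. k = 3 gives p = 0.083; k = 4 gives p = 0.0455.

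Neither threshold depends on N.

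**Step 2: rejection probability under that coding.** The number reporting relief is Binomial(N, p). The test rejects when it is at least 6 (exact) or 4 (chi-square). Entries are exact / chi-square.

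| N | p = 10% | p = 20% | p = 30% |
|---|---|---|---|
| 10 | 0.000 / 0.013 | 0.006 / 0.121 | 0.047 / 0.350 |
| 20 | 0.011 / 0.133 | 0.196 / 0.589 | 0.584 / 0.893 |
| 30 | 0.073 / 0.353 | 0.572 / 0.877 | 0.923 / 0.991 |
| 60 | 0.563 / 0.863 | 0.988 / 0.999 | 1.000 / 1.000 |

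If nobody reports relief, the test never rejects.

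**Step 3: Group B's pre value is its post-Biotene rating, and Group A is set to no relief.** Half of the subjects are in each group, both products are inert with the same rate p, and ratings are independent (200,000 simulated trials). At N = 30, exact / chi-square rejection is 0.02 / 0.10 at p = 10%, 0.09 / 0.16 at 20% and 0.17 / 0.24 at 30%. At N = 60 and 30% it is 0.41 / 0.51. This version also mixes product-versus-nothing in Group A with product-versus-product in Group B.

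**Step 4: the same item is really asked before and after, and nothing shifts.** With rate p at both times and independent answers, each direction of discordance has probability p(1 − p). Enumeration over N = 10 to 60 and p = 10% to 40% gives at most 0.030 (exact) and 0.010 to 0.054 (chi-square), which is about nominal.

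**Step 5: no pre value is recorded or imputed.** There are no pairs, and the test cannot be run.

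**Step 6: is rewording the item enough?** No. Suppose a symptom item is asked both times and expectation moves 30% of subjects from dry to not dry, with none moving back. The discordant pairs then have the same distribution as in Step 2, so the exact test rejects in 58% of trials at N = 20 and 92% at N = 30. Any reverse changes would lower this. In the MI Paste versus Biotene comparison, by contrast, a non-specific rate shared by both products gives the symmetric set-up of Step 4, with error about nominal.

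**The case against.** A reader might infer that relief is a post-product rating only, and hence that the test is likely to be significant even if MI Paste does nothing. The documents do not support that. The inference rests on one noun; the item wording is not given, and nothing says that a missing pre value is coded as no relief. The SAP puts relief in the same phrase as denture fit and function, under tests that require two recordings of the same categories. It also implies a baseline for comfort and retention. Dry mouth relief may be loose wording for an item asked at both times, in which case Step 4 applies if nothing shifts.

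Even under the fixed coding, rejection is not near-certain across the range: at 10% non-specific relief the exact test rejects in 1% of trials at N = 20 and 7% at N = 30. Group B may also have a real rating just before MI Paste. And dry mouth relief is neither one of the four listed primary outcomes nor the stated aim.

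All of this stands, and it limits the error-rate argument to a conditional one. It does not supply the missing definition of the pre value. Nor does it answer the point that a one-product pre/post contrast, with no blinding described, cannot attribute a change to the product.

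**Conclusion.** The point holds in conditional form. The plan specifies a paired test on an item whose pre-MI Paste value is undefined, in a schedule that describes only post-product questionnaires.

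The size depends on how pre is filled. With 20% to 30% non-specific relief and N of 20 to 30, exact rejection with an inert product is 20% to 92% if pre is fixed at no relief. At N = 30 and the same rates, it is 9% to 17% if only Group A is so fixed. It is at most 3% if a real rating is taken and nothing shifts. N, the relief rates, the binary item and independence of ratings are assumptions.

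What does not depend on these assumptions is interpretation: under every reading, the named test leaves the randomised product comparison unused and cannot show that MI Paste itself relieved dry mouth. This merits a change to the SAP, but it does not bear on the four listed primary outcomes.

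**What to change.** In the SAP sentence, make the dry mouth test a within-subject MI Paste versus Biotene comparison of the post-product ratings. Use McNemar's or Bowker's test and account for period, for example with the Mainland-Gart form for a binary item. State the item, its categories and its reference period.

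Run a pre/post test only on a dry mouth symptom item asked in identical words before the first product and after each product, and label it as uncontrolled. Report relief descriptively by product. Do not test it against an imputed pre-application value.

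The product comparison has limits that should be stated. It estimates a difference between two products, not an effect against no treatment. It does not remove expectation that differs between the products. With no washout described, it also relies on little carry-over.

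The cost is one rewritten sentence, a little extra analysis and, if not already collected, one symptom item. Both post-product questionnaires are already planned. The sponsor gives up a relief p-value that would more easily reach significance.
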